- 13. Must be willing to comply with all study protocol requirements (pay attention to: only use the skin care products provided during the study, not take topical or oral treatment like retinol, hormone, anti-oxidant health-care products which may affect the anti-aging efficacy of test serum).

Exclusion Criteria:

Prospective subjects meeting any of the criteria listed below will be excluded from participation:

- 1. Pregnant or breast-feeding woman or woman planning pregnancy during the study.
- 2. Subject deprived of rights by a court or administrative order.
- 3. Major subject to a guardianship order.
- 4. Subject residing in a health or social care establishment.
- 5. Patient in an emergency setting.
- 6. Subject with a skin disease in the test areas as well as skin allergy (particularly e.g., acne, rosacea, eczema).
- 7. Volunteer presenting a stable or progressive serious disease (per investigator's assessment).
- 8. Immuno-compromised subject.
- 9. Subject has hyperpigmentation skin symptoms.
- 10. Subject with history of allergy to cosmetic or personal care products or ingredients.
- 11. Subject presenting excessive exposure to sunlight or UV radiation (investigator's assessment).
- 12. Subjects regularly practicing aquatic or nautical sports.
- 13. Subjects regularly attending a sauna.
- 14. Subject with physical highly sensitive constitution;

¹Declaration of Helsinki, 64th World Medical Assembly, Fortaleza, Brazil, October 2013

- 15. Subject with cardiovascular or circulatory history.
- 16. Subject with a history of skin cancer or malignant melanoma.
- 17. Subject with history of medical beauty treatment and taking part in anti-aging studies in the last 3 months before study.
- 18. Intake of antihistamines, antibiotics, corticosteroids, non-steroidal anti-inflammatories or immune-suppressants in the last 6 months before study.

4. Study Design

70 female adult subjects will be enrolled and divided into 2 groups in the study, recruited according to inclusion and non-inclusion criteria listed below, and at least 60 subjects should complete the whole study (at least 30 subjects per group).

• Clinical Assessment(N=60):

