8.1. Statistical considerations

All statistical tests will be two-sided and at the 5% level of significance.

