8.3. Efficacy Verification

8.3.1 Comparison between Time-points

A Shapiro-Wilk test will be used to test for normality of the baseline data (T0) and the change from baseline data (Tn-T0) at post-baseline time points at significance level alpha=0.01. When data passes normality (all normality of the distributions is confirmed for the same parameter), a parametric test will be used to test the null hypothesis that the mean change from baseline is zero. When data fails normality (if one or more normality of the distributions for the same parameter is rejected), a non-parametric test will be used.

Pre-treatment efficacy:

- a) T14d (after pre-treatment), T15d (Timm post-procedure) versus T0 (baseline)
- b) T16d (1-day after self-recovery), T18d (3-day after self-recovery), T22d (7-day after self-recovery), T25d (10-day after self-recovery) versus T15d (Timm post-procedure)

Post-treatment efficacy:

a) T32d (7-day after product treatment), T39d (14-day after product treatment) versus T25d (product treatment start)

The following will be calculated and reported for each evaluation parameter at applicable post-statistical baseline time point(s):

For self-assessment questionnaires, only the data of completing subjects will be analyzed. Questionnaire response options will be in the form of a 5-point semi-structured scale, ranging from one (1) to (5), where the score of one (1) will be the most negative/unfavorable rating and the score of five (5) will be the most positive/favorable rating the product can receive (the scale will also include a mid-point label "neither agree nor disagree"). Responses obtained for each question will be tested for normality using a Shapiro-Wilk test at significance level alpha=0.01, and if the data passes normality testing, mean scores will be used. Responses that are not normally distributed will be assessed using the median response. The percentage of ratings from

4 to 5 ("top XX box %") will be reported.

In the report appendices, raw data and open-ended questionnaire responses will be listed by subject. Data frequency and percentage will be presented for questionnaires and tolerability evaluations. Tolerability tables will also be sent to the Sponsor at the indicated interim data time points; SAQ data will be sent at study completion, for all completing subjects. Medians, means and percentage values will be reported to decimal place (0.0) for all questionnaire data.

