A more appropriate analysis may be performed, which will be recorded in a Note to File and/or in the study report.

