8.3.2 Comparison between Treatments

Paired T test for the same sample size or the independent T test for the different sample size will be used to identify the difference efficacy between treatments if the data fit normal distribution.

- Group 1-Facial Serum group
- **Group 2-**Non-treatment control group

Evaluation	Attributes	Comparison
Clinical Assessment	•Skin symptoms scoring post-procedure: - Dryness - Erythema - Papules - Desquamation - Chromatosis - Edema - Escharosis •Skin qualities: - Skin elasticity - Skin evenness - Skin brightness - Skin smoothness - Skin radiance - Appearance of pores on cheek - Crow's feet wrinkle - Epithelial cell confluence - Over healthy appearance	Group 1 versus Group 2
Instrumental Assessment	Skin hydration by Corneometer Transepidermal water loss (TEWL) by Vapometer Skin elasticity by Cutometer Skin pH by Skin-pH-Meter	
Imaging Analysis	Attributes output from VISIA 7 Attributes output from OCT (The thickness of epidermis)	
LA stinging Test	•Skin symptoms scoring: - Stinging - Itching - Burning	
Tolerance Feedback	•Skin symptoms scoring: - Area - Severity - Start time - During time	

9. Further Study Documentation

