Annex 11.4. DIARIES for Tolerance Feedback in Daily

RD Number:	Subject Initial:	

				Without	Skin Irritation 皮肤有反应时填写				
				Irritation	Symptom 出现的症状	Area 症状发生的部位	Severity 症状的程度	Start Time 症状开始时间	During Time 症状持续时间
		Date(Y/M	/ D)	(√)	1. Redness 发红	出现的症状在哪些部	1. Very slight	使用产品后多长时间皮肤	
No.	Treatment	日期(年/	/月/	未发生任	2. Dryness 干燥	位? 1. Eye 眼部	非常轻微	开始有反应? 1. Immediate 用后立即	How long is the
序号	产品	日)		何不良的	3. Stinging 刺痛 4. Itching 瘙痒	2. Forehead 额头	2. Slight 轻微 3. Moderate 中	2. 30mins after using 用	irritation
		使用后填	海	情况	5. Tightening 紧绷感	3. Cheek 脸颊 4. Lip corner 嘴角	度	后 30 分钟内 3. 30mins to several	lasting? 皮肤反应的特
				(请打钩)	6. Burning 发热/灼烧 感	5. Chin 下巴	4. Extensive 重 度	hours after using 用后	征持续了多长 时间?
				(M3 11 M3)	7. Others(specific) 其 他 (请注明)	6. Others(specific) 其他 (请注 明)	5. Very severe 非常严重	30 分钟至几个小时 4. Several days after using 用后天	HJ PJ
D1			早						
			晚						
D2			早						
			晚 早						
D3		F	晚						
			早						
D4		F	晚						
D5			早						
DS			晚						
D6		-	早						
			晚 早						
D7		-	晚						
			早						
D8		-	晚						
D9			早						
D9			晚						
D10			早						
			晚 早						
D11			晚						
			早						
D12			晚						
D13			早						
מוט			晚						
D14			早						
			晚						
D15~ D56			早						
D56			晚						

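### The between-group diary comparison uses fields completed only when the skin reacts, so unless non-reactors are scored zero it does not test whether more women react with the serum

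*Protocol*

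**What the plan says.** The table in protocol section 8.3.2 lists what is compared between Group 1 (serum) and Group 2 (no serum). For tolerance feedback the attributes are "Skin symptoms scoring: - Area - Severity - Start time - During time". The test is fixed in the same section, for normally distributed data: "Paired T test for the same sample size or the independent T test for the different sample size will be used". Section 8.1 adds: "All statistical tests will be two-sided and at the 5% level of significance".

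The four attributes are columns of the daily diary in Annex 11.4. There they stand, with the symptom column, under the header "Skin Irritation 皮肤有反应时填写"; the Chinese tells the woman to complete this part when her skin reacts. Severity is graded from 1 (very slight) to 5 (very severe). A woman with no reaction ticks a separate column for no irritation.

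Section 8.3.1 also plans descriptive output: "Data frequency and percentage will be presented for questionnaires and tolerability evaluations". It attaches no between-group test to that output. It closes with a general allowance: "A more appropriate analysis may be performed, which will be recorded in a Note to File and/or in the study report".

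**The concern.** The tolerance question in a serum v no-serum comparison is first of all whether more women react when they use the serum. The only diary field that answers this for every woman, the no-irritation tick, is not among the compared attributes. The four that are listed hold a value only if a reaction occurred.

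Read as written, the null hypothesis is that severity, duration and so on are equal among women who reacted. Two things follow.

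- A difference in incidence is outside the hypothesis being tested.
- Whether a woman reacts is determined after randomisation and may be caused by the serum. The reactors in the two groups are therefore not randomised counterparts, and a difference between them is hard to interpret in either direction.

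At stake is the one formal between-group statement on diary tolerance. A non-significant result could be reported as equal tolerance when it says nothing about how many women were affected.

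**Working it through.** **No figure to reproduce.** The protocol gives no power calculation and no expected reaction rate.

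**Inputs from the protocol.** At least 30 completers per group (section 4); two-sided 5% level (8.1); t-test between groups (8.3.2; the independent form is used here, since reactor counts will usually differ); severity levels 1 to 5 with no zero (Annex 11.4).

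**Assumptions.** Reaction rates of 10% to 60%. One severity value per woman. The same severity spread among reactors in both groups, 40/30/20/7/3% on levels 1 to 5.

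**How many women enter the comparison.** At a 10% rate, Group 2 supplies on average 30 × 0.10 = 3 women. The chance of fewer than two is 0.9^30 + 30 × 0.1 × 0.9^29 = 0.042 + 0.141 = 0.184 (rounded from unrounded terms), so in about 18% of trials a t-test cannot sensibly be computed.

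**Simulation, 5,000 runs per row.** Entries are the percentage of runs with p < 0.05. Runs where the reactor-only test could not be computed count as non-rejections.

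| Reactors, Group 1 v Group 2 | t-test, reactors only | Not computable | t-test on severity, non-reactors = 0 | Fisher's test on incidence |
|---|---|---|---|---|
| 10% v 10% | 2.9 | 33.7 | 3.4 | 1.0 |
| 30% v 10% | 4.1 | 18.2 | 40.4 | 37.8 |
| 40% v 10% | 3.5 | 18.7 | 67.7 | 70.9 |
| 50% v 10% | 3.6 | 18.3 | 86.9 | 91.6 |
| 60% v 20% | 5.1 | 0.9 | 76.7 | 84.5 |

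**Sensitivity to the severity spread.** With 35/35/20/8/2%, the reactor-only and Fisher results agree within simulation error. The zero-coded t-test at 40% v 10% is about 69%. A rank test on severity with non-reactors at 0 rejects in about 49%, 78–79%, 94% and 88% of runs for the last four rows in order.

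**What the table shows.** The reactor-only column does not move with incidence. That is by construction: severity among reactors was set equal, so this test's own null is true. The column illustrates which question the test asks; it is not evidence of a faulty t-test.

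**A case where severity differs.** Suppose 50% react in Group 1, mostly slightly (70/20/10/0/0%), and 20% react in Group 2 (35/35/20/8/2%).

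- Mean among reactors: Group 1, 0.70×1 + 0.20×2 + 0.10×3 = 1.40; Group 2, 0.35×1 + 0.35×2 + 0.20×3 + 0.08×4 + 0.02×5 = 2.07. The serum looks milder.
- Mean over all women with 0 for none: Group 1, 0.50 × 1.40 = 0.70; Group 2, 0.20 × 2.07 = 0.41. The serum looks worse.

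In simulation the reactor-only mean favours the serum in about 92% of runs.

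**The case against.** The strongest reply is that section 8.3.2 names attributes but not an analysis population. It does not say that non-reactors are dropped. A tick for no irritation is a positive record, and scoring it 0 is an ordinary derivation that an SAP could contain. This stands in part: with that coding, the severity comparison recovers most of the power (about 69% at 40% v 10%). It does not rescue the list as a whole. Area is a location code and start time a delay after use; neither has a value for a woman who did not react. And the protocol is not silent here: it chose the fields to compare and left out the one that records whether a woman reacted. The row's label refers to scoring of symptoms, so whether the symptom column is meant to be included is unclear.

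A reader might infer that the trial cannot detect an excess of reactions. The protocol does not support that. Section 8.3.1 tabulates tolerability frequencies, and section 7.2 checks adverse events and local intolerance at every visit. Section 8.3.2 also compares dermatologist scores such as dryness, erythema and edema, and lactic-acid stinging, itching and burning; sections 5.1 and 5.2 anchor these at 0 for all women. A large excess could show in any of these. They are visit-based or descriptive, so they do not replace a diary test.

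A reader might also infer that the trial's tolerance conclusion will have the wrong sign. That reversal needs an assumed shift towards slight reactions and concerns this diary comparison alone. If the serum instead made reactions more severe or longer, the listed fields could pick that up, though still not the number of women affected.

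The allowance for a more appropriate analysis does not repair the list: it names no alternative and can be used after the data are seen.

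**Conclusion.** The point holds for the formal diary comparison in section 8.3.2 and no further. Unless non-reactors are given a zero, which the protocol does not state, that comparison is confined to reactors, conditions on a post-randomisation event and does not test incidence. For illustration, at 40% v 10% reactors with equal severity among them, it rejects in about 4% of runs where Fisher's test on incidence rejects in about 71%. The size rests on assumed reaction rates, an assumed severity spread, one severity value per woman and blank fields being treated as missing. The structural point, that the compared fields leave out whether a woman reacted, needs none of the assumed rates. It should be corrected, but the trial's other tolerance outputs remain usable.

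**What to change.** In the tolerance feedback row of section 8.3.2:

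1. Add the proportion of women with any diary-recorded irritation in each product-use period (T0 to T14d and T25d to T39d), over all women in each group, compared by Fisher's exact test with a 95% confidence interval for the difference.
2. Analyse worst severity per woman over all women, with 0 for no irritation, by a rank test.
3. Report area, start time and duration among reactors descriptively, without a between-group p-value.

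Stating only that non-reactors score 0 for severity and duration would be a smaller repair, but it leaves area and start time unresolved.

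The cost is a change of wording. The diary already collects everything needed, so no visit, measurement or subject is added. The small downside is the loss of between-group p-values on area, start time and duration.

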9.1. Protocol Amendment

Any protocol amendment (Annex 11.5) signed by mutual agreement is documented.

9.2. Dropouts

Subjects may withdraw from the study at any time. In the case of withdrawal, the reason of withdrawing is documented and reported.

9.3. Deviations from Protocol

Protocol deviations (Annex 11.6) are documented and reported.

9.4. Adverse Event Reporting

Unexpected or unusual medical events or clinical symptoms are documented in an adverse event form (Annex 11.7). The subjects are instructed to immediately contact the test site to be examined by the investigator and/or designee. If this event is a medical condition that is not part of the subject's medical history, it is documented.

The investigator or designee will notify the sponsor representative of any adverse events (within 24 hours) or any severe adverse events (immediately) or any events that are related to study participation.

10. Ethical Considerations

According to this study (protocol, ICD/Assent Document, and all addenda) will be reviewed and approved by an Ethic contacted by the Study Site.

Details of the Ethic for this study are indicated below:

- Name: Independent Ethics Committee, Shanghai Clinical Research Center
- Address: [name]
- Contact details: [name], [contact]

It is the responsibility of the PI to have Ethic approval of the study protocol, protocol amendments, ICD/Assent Document(s), and other relevant documents, e.g., advertisements, as applicable.

The study will not be activated and subjects will not be recruited, consented, or receive study materials until such time as the Ethic has approved the required documentation. In addition, the Ethic will review the study before any significant change in the protocol is initiated. After each review, the Ethic's approval letter will be forwarded to the Sponsor. All correspondence with the Ethic should be retained in the study master file to storage.

11. Annex

- 11.1 Subject Eligibility Check List
- 11.2 Hyperpigmentation Skin Questionnaire
- 11.3 Self-assessment Questionnaire
- 11.4 DIARIES for Tolerance Feedback in Daily
- 11.5 Protocol Amendment Document
- 11.6 Protocol Deviation Record
- 11.7 Adverse Event Report Form

Annex 11.1. Subject Eligibility Check List

Tes	st No.: Volunteer No.:	Sex: female male	Age:			
1.	Chinese women, 20-50 years old;			yes		no
2.	All skin types (dry, normal, oily and mixed);			yes	\Box	no
3.	Rough ad dull skin by self-declared;	Ħ	yes	H	no	
4.	Lack of radiance, brightness, smoothness by self-or		H	yes	H	no
5.	Presenting with problems of acne mark, acne scar	or blemishes on face;		yes		110
6.	Did not participate any clinical test or cosmetic pro-					
7.	Did not participate any chemical procedures for pr					
_	participate any procedures during the whole study					
8.	Did not participate any clinical test or cosmetic pro			MOC		no
9.	No disagreement of dermatologist because of participation of the volunteer.	other reasons that exclude the	Ш	yes	Ш	no
10.	In general good health at the time of the study.					
11.	Willing and able to participate as evidenced by sign	gning of informed consent?				
12.	Must be willing to comply with all study protocol	•				
13.	Are you in general good health at the time of stud	y? -		yes		no
14.	Are you willing and able to participate as evidence	ed by signing of informed consent?		yes		no
15.	Are you intending to get pregnant, in pregnancy,	lactation or the periodof 6 months		MOC		no
	after childbirth?			yes		no
16.	Do you take part in another study, which is carried		Ш	yes	Ш	no
17.	Do you have known allergies against skin / hair calcohol?	eare product or topical medicine or		yes		no
18.	Do you have any other serious illness or diseases?			yes		no
19.	I have read theen closed "Information forVoluntee	ers" with fully understanding.		yes		no
20.	The possibility of adverse reactions occurred by a					
	sufficiently and scientifically foreseen. Your safet	•				
	our ability. But during the study or the latter part of					
	adverse reactions caused by force majeure, which medical institutes. Do you fully understand and ag			yes		no
21.	I have been fully informed about the implement, e		Ш	yes	ш	110
	study. I voluntarily take part in this study; my data					
	relevant departments, institutes or firms. Details a		_		_	
	secrecy. I'm not allowed to pass them to anyone.			yes	Ш	no
22.	Your name or other personal information will not					
	anonymously passed to relevant government depa If the facial image capture is taken in the project a					
	other academic purposes, and your facial images r					
	measures (for example, add a black bar to cover the					
	guarantee that you will not be identified. Do you f			yes		no
23.	I have read and understood all above asked question	ons and answered them truth fully.		yes		no
_		Date:				
Kest	oonsible Tester: I	Oate:				

Annex 11.2. Hyperpigmentation Skin Questionnaire

Hyperpigmentation Skin Questionnaire

色素沉着性皮肤问卷

Q1. When having acne, dark brown/ black marks usually left on skin surface:

长过痘痘后的部位会留下深棕色/黑色的印记:

A. Never

从不

B. Sometimes

有时会

C. Often

经常会

D. Always

总是这样

E. Never having acne

我从没长过痘痘

Q2. When having skin scratch, the brown marks usually last:

被割伤后, 棕色的印记(不是新愈合时粉色的疤)会残留多久:

A. None marks

不会留下疤痕

B. 1 week

1周

C. Several weeks

几周

D. Several months

好几个月

Q3. Taking oral contraceptive pills or other hormone replacement or in duration of pregnancy, dark spots usually appear:

当你怀孕、服用口服避孕药丸或其他荷尔蒙替代类药物时,脸上会长出深色斑点:

A. None spot

没有斑点

B. One spot

1个

C. A few spots

少量

D. Many spots

很多

Q4. Dark spots/patches on your upper lip or cheeks:

你的上唇或面颊有深色斑点/块吗?

A. None

没有

B. Not sure

我不确定

C. Yes, slightly

是的,一点明显

D. Yes, obviously

是的,非常明显

Q5. Sunburn gets worse after skin exposure in the sun:

日晒之后斑点会加深:

A. None sunburn

我没有深色斑点

B. Not sure

无法确定

C. A little

有点加深

D. Much worse

变深很多

E. Never having skin exposure in the sun

我从不直接接触阳光

Q6. Your facial skin has been diagnosed with pigmentation or light/dark brown/gray spots:

你的面部皮肤曾经被诊断为有色素沉积、或有浅/深棕/灰色斑:

A. Never

没有

B. Once

有一次

C. Yes, but it disappeared.

是的,但是后来消失了

D. Yes, but it never disappeared.

是的, 仍然存在

E. Not sure

无法确定

Q7. Having or ever had small brown spots (freckles or sunburn) on the face, chest, back or arms:

脸部、前胸、后背或手臂是否有或者曾经有小的棕色斑点(雀斑或晒斑):

A. None

没有

B. Several (1-5 spots)

有一些 (1-5 个)

C. Some (6-15 spots)

有很多(6-15个)

D. Many (more than 16 spots)

非常多(16个以上)

Q8. First time skin exposure in the sun in several months (e.g., early spring or summer), your skin feels: 几个月来第一次晒太阳(例如刚入春或入夏),皮肤感觉:

A. Burning

灼热

B. Burning and dark marks appear thereafter

灼热然后变黑

C. Dark marks appear immediately

直接变黑

D. Not sure. I have dark skin.

我也分不清, 我的肤色已经很深了

Q9. Skin exposure in the sun for several days:

连续数天暴露于阳光下:

A. Burning and blister, but it doesn't affect my skin tone.

灼热甚至起泡, 但我的肤色没有什么变化

B. Skin tone gets slightly darker

肤色变深了一点

C. Skin tone gets much darker

肤色变深了很多

D. Not sure. I have dark skin.

我也分不清, 我的肤色已经很深了

Q10. Insolation leads freckle appearance:

日晒有没有引起雀斑

A. Never

我从没长过雀斑

B. Sometime

偶尔长出一些

C. Often

经常长出一些

D. Not sure. I have dark skin.

我也分不清, 我的肤色已经很深了

Q11. If any of your family member has freckle on face, please describe the severity:

你的父母中有人长雀斑吗?如果有,请描述程度。

A. None 没有 B. Some 有一些 C. Many 有很多 D. Many on face, chest, back, neck and shoulders 脸上、前胸、后背、颈脖肩膀都有很多 E. Not sure 不确定 Q12. Your nature hair color: 你的天然发色是: A. Red 红色 B. Black 黑色 C. Brown 棕色 D. Blond 金色 Q13. The history of melanoma among family members: 家庭的直系亲属中是否有黑素瘤病史: A. None 没有 B. Only one family member 有一个人 C. More than one family member 一人以上 D. I have a history of melanoma. 我自己有黑素瘤病史 E. Not sure 不确定 Scoring criteria: 评分: A: 0p B: 1p C:2p D:3p E: 1p A: 0 分 B: 1 分 C:2 分 D:3 分 E:1分 ≤ 14p Low risk of pigmentation inducement 低色素沉着风险 Medium risk of pigmentation inducement 15p-27p

中色素沉着风险

28p-44p High risk of pigmentation inducement

高色素沉着风险

Annex 11.3. Self-assessment Questionnaire

Answers given according to a 5-point scale: "5-completely agree 非常同意", "4-somewhat agree 比较同意""3-neither agree 说不上同意不同意", "2-somewhat disagree 比较不同意", "1-completely disagree 非常不同意"

Self-assessment - Pre-treatment	Yes/是	No/否	Comments/ 其他
术前 14 天产品使用问卷			, -
I feel skin is good prepared for procedure			
我觉得我的肌肤更强韧了,为特殊美容做好了准备			
I feel skin is comfort for procedure			
我觉得我的皮肤在特殊美容中更耐受了			
Skin feels intensively repaired			
肌肤感觉被深层修护			
I feel skin redness due to dryness is less occur?			
我感觉皮肤由于干燥而发红的情况减少了			
Skin feels strengthened			
肌肤感觉更强韧			
Skin feels hydrated			
肌肤感觉水润保湿			
Skin feels comfortable			
肌肤感觉舒服			
Skin feels smoother			
肌肤感觉更光滑			
Skin looks brighter			
肌肤看起来更明亮			
Skin looks more radiant			
肌肤看起来更有光泽			
Pores look less visible			
毛孔看起来不明显			
Skin feels more elastic			
肌肤感觉更有弹性			
Fine line looks less visible			
细纹看起来不明显			
Crow's feet wrinkle is reduced			
鱼尾纹看上去减少了			
Self-assessment - Recovery			
术前后 1 天,3 天,7 天,10 天恢复			
期问卷			
I feel pre-treatment with product help my skin recover fast			
after procedure			
我感觉提前14天使用产品,可以帮助肌肤在特殊美容后更			
快修复			
I feel pre-treatment with product help my skin recover			

		T
stable after procedure		
我感觉提前 14 天使用产品,可以帮助肌肤在特殊美容后更		
稳定		
I feel pre-treatment with product help my skin recover		
comfortable after procedure		
我感觉提前14天使用产品,可以帮助肌肤在特殊美容后更		
舒适		
I feel pre-treatment with product help my skin redness		
recovered		
我感觉提前14天使用产品,可以帮助肌肤在特殊美容后褪		
红		
I feel pre-treatmet with product help my skin dryness		
recovered		
我感觉提前14天使用产品,可以帮助肌肤在特殊美容后降		
低干燥爆皮		
I feel pre-treatment with product help my skin discomfort		
(e.g. red/dry/itch) from procedure recovered faster		
我感觉提前14天使用产品,可以使肌肤在特殊美容后的不		
适症状(如发红/干燥/瘙痒等)更快修复		
I would like to recommend my friends to use product before		
procedure		
我很乐意推荐我的朋友们,在特殊美容前使用产品		
I feel skin is comfort for procedure		
我觉得我的皮肤在特殊美容中更耐受了		
Self-assessment		
- Post-treatment		
术前7天及14天产品使用问卷		
Post-treat with product after skin recovered, skin feels		
smoother		
当肌肤在特殊美容恢复后,使用产品,肌肤感觉更光滑了		
Post-treat with product after skin recovered, skin feels		
brighter		
当肌肤在特殊美容恢复后,使用产品,肌肤感觉更明亮了		
Post-treat with product after skin recovered, skin feels		
more radiant		
当肌肤在特殊美容恢复后,使用产品,肌肤感觉更有光泽		
7		
Post-treat with product after skin recovered, skin pore is		
less visible		
当肌肤在特殊美容恢复后,使用产品,毛孔看起来不明显		
7		
Post-treat with product after skin recovered, skin feels		
more elastic		
当肌肤在特殊美容恢复后,使用产品,肌肤感觉更有弹性		
一元の1年197677日の久川・区川・田・地域へ80万円円	 	

	ı	
Post-treat with product after skin recovered, fine line looks		
less visible		
当肌肤在特殊美容恢复后,使用产品,细纹看起来不明显		
了		
Post-treat with product after skin recovered, crow's feet		
wrinkle is reduced		
当肌肤在特殊美容恢复后,使用产品,鱼尾纹看起来不明		
显了		
Post-treat with product after skin recovered, skin feels		
intensively repaired		
当肌肤在特殊美容恢复后,使用产品,肌肤感觉被深层修		
复		
Post-treat with product after skin recovered, skin feels		
strengthened		
当肌肤在特殊美容恢复后,使用产品,肌肤感觉更强韧了		
Post-treat with product after skin recovered, skin feels		
hydrated		
当肌肤在特殊美容恢复后,使用产品,肌肤感觉水润保湿		
Post-treat with product after skin recovered, skin feels		
comfortable		
当肌肤在特殊美容恢复后,使用产品,肌肤感觉舒适		
I would like to recommend my friends to use product for		
post-treat		
我很乐意推荐我的朋友们,在特殊美容后使用产品		

